5.4. Secondary Endpoints Analysis

All secondary endpoints will be analyzed for the ITT set.

5.4.1. Intrahepatic Secondary Endpoints

As a general consideration, no imputation rule will be applied in case of missing biopsy assessment or insufficient biopsy sample material required to obtain the individual intrahepatic markers at baseline and/or Week 12 and/or Week 40. Some imputation rule may be applied for specific endpoints and will be described in the relevant section(s).

5.4.1.1. Intrahepatic Immune Response

5.4.1.1.1. For Panels 1 and 2

The following immune cells will be evaluated:

- CD45+ T-cells,
- CD4+ T-cells,
- CD8+ T-cells,
- Natural Killer (NK) cells,
- Dendritic cells

Additional immune cells may be explored.

Estimations on change in proportions using a similar mixed model as described in Section 5.3.1.2.2 with an appropriate distribution for each type of cells will be provided. It may differ from the assumption of binomial distribution made for the primary endpoint.

In addition, similar summary statistics and graphical displays on the calculated change in proportion will be provided as defined in Section 5.3.1.2.3. Additional immune cells may be evaluated depending on data availability and clinical interest. Spatial distribution for each cell type at baseline and Week 40 will be graphically evaluated.

5.4.1.1.2. For Panel 3

The same immune cells as described in Section 5.4.1.1.1 may be analyzed for Panel 3 at Week 12 and Week 40. Descriptive analyses may be provided as defined in Section 5.3.1.2.3.

5.4.1.2. Intrahepatic Viral Parameters

5.4.1.2.1. For Panels 1 and 2

Descriptive statistics on actual values at baseline and Week 40 and changes from baseline at Week 40 will be summarized for the following parameters:

- Number and proportion of cccDNA-positive hepatocytes
- Number and proportion pgRNA-positive hepatocytes
- Number and proportion of silent hepatocytes
- cccDNA levels (positive/negative)
- pgRNA levels (positive/negative)

Number of cells will be expressed in original unit and proportions or ratios will be provided in both original and \log_{10} transformed scales. Change from baseline will be provided in \log_{10} transformed unit. In addition, same graphical displays as described in Section 5.3.1.2.3 will be provided.

5.4.1.2.2. For Panel 3

The number and proportion of HBsAg+ hepatocytes, as well as the same viral parameters described in Section 5.4.1.2.1, may be provided at Week 12 and Week 40, depending on the availability of biopsy material.

5.4.2. Blood Peripheral Secondary Endpoints

5.4.2.1. HBsAg Seroclearance

HBsAg seroclearance, defined as quantitative HBsAg <LLOQ (see Table 3), will be evaluated at all time points.

If the HBsAg value at Weeks 40 or 48 is missing, the LOCF approach will be used with the condition that no value more than 8 weeks prior to the respective time point may be carried forward. At FU Weeks 12, 24, 36 and 48, and at 24, 36, and 48 weeks after stopping all study

interventions, if an HBsAg value is missing, then LOCF approach will be used with the condition that no value more than 12 weeks prior to the respective time point will be used. For all other time points, seroclearance will be analyzed as observed case without imputation.

The proportion of participants who achieve HBsAg seroclearance over time will be summarized.

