**Definitions of Terms**

Study intervention	Prior to Protocol Amendment 5: JNJ-73763989 (JNJ-3989), JNJ-56136379 (JNJ-6379) and NA (either ETV, tenofovir disoproxil, or TAF) As of Protocol Amendment 5: JNJ-73763989 (JNJ-3989) and NA (either ETV, tenofovir disoproxil, or TAF)
Functional cure	HBsAg seroclearance 24 weeks after end of treatment
HBsAg or HBeAg seroclearance	HBsAg or HBeAg negativity, respectively, based on the assay used
HBsAg or HBeAg seroconversion	HBsAg or HBeAg negativity and anti-HBs or anti-HBe antibody positivity, respectively
Virologic breakthrough	Confirmed on-treatment HBV DNA increase by $>1 \log_{10}$ IU/mL from nadir or confirmed on-treatment HBV DNA level $>200$ IU/mL in participants who had HBV DNA level $<\text{LLOQ}$ of the HBV DNA assay
ALT/AST nadir	Lowest ALT/AST value during study participation

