5.4.2.3. HBeAg Seroclearance and Seroconversion

Seroclearance of HBeAg is defined as (quantitative) HBeAg <LLOQ. The HBeAg seroclearance will be summarized only for HBeAg positive participants at study entry.

Seroclearance will be analyzed as observed case without imputation and with imputation using LOCF approach. For the imputation with LOCF approach, we impute the missing data with the following restriction. If the HBeAg value at Weeks 40 or 48 is missing, the LOCF approach will be used with the condition that no value more than 8 weeks prior to the respective time point may be carried forward. At FU Weeks, if an HBeAg value is missing, then LOCF approach will be used

with the condition that no value before the FU phase or more than 12 weeks prior to the respective time point will be used. For all other time points, seroclearance will be analyzed as observed case without imputation.

The proportion of participants who achieve HBeAg seroclearance over time will be summarized.

Seroconversion of HBeAg is defined as having achieved HBeAg seroclearance together with appearance of anti-HBe antibodies. Appearance of anti-HBe antibodies is defined as a baseline anti-HBe antibodies (qualitative) with a "NEGATIVE" result and a post-baseline assessment with "POSITIVE" result. The seroconversion of HBeAg will be summarized only for HBeAg positive participants at study entry.

The seroconversion will only be assessed at the time points when the anti-HBe antibodies assessment is available. If the HBeAg value is missing at that specific time point, then the non-missing lab test closest to that specific timepoint will be used. If the non-missing lab test before and after the specific timepoint fall equidistant from the target timepoint, the later one will be used to impute the missing value.

The number and proportion of participants who achieve HBeAg seroconversion will be summarized.

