5.4.2.5. Functional Cure

A participant will be defined as having achieved Functional Cure (FC) at a given time point during the FU phase if he/she has HBsAg seroclearance (as defined in Section 5.4.2.1) at that time point and has stopped all study interventions (including NA and PegIFN- α 2a) for at least 24 weeks without re-treatment.

Participants who discontinue treatment prior to Week 48 (except for JNJ-6379), or who withdraw from the study prior to the given time point, will be considered as non-responders for FC in this study. The CRF pages of ‘Treatment Disposition of JNJ-3989’, ‘Treatment Disposition of NA Treatment’, ‘Treatment Disposition for NA Re-Treatment’ and ‘Treatment Disposition for PegIFN-alpha2a’ will be checked to ensure all treatment actually stopped.

Subjects still in the study at a given time point but with missing HBsAg assessment at that time after implementation of LOCF (as described in Section 5.4.2.1), will be considered as non-responders.

Number and proportion of participants achieving FC will be summarized at 24, 36, and 48 weeks after stopping all study interventions (including NA and PegIFN- α 2a). Subjects who never reach such time points will be considered as non-responders.

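### The HBsAg carry-forward rule lets a 12-week off-treatment value count as functional cure at 24 weeks, and it lacks the HBeAg rule's bar on values from before follow-up

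*SAP*

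**What the plan says.** SAP 5.4.2.1 defines seroclearance as quantitative HBsAg below the LLOQ (0.05 IU/mL in SAP Table 3) and sets two carry-forward limits. At Weeks 40 and 48, "no value more than 8 weeks prior to the respective time point may be carried forward". Later the limit is longer: "At FU Weeks 12, 24, 36 and 48, and at 24, 36, and 48 weeks after stopping all study" interventions, a missing value may be replaced by the last available one as long as "no value more than 12 weeks prior to the respective time point will be used".

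SAP 5.4.2.5 defines functional cure as seroclearance at a time point when everything has been stopped "for at least 24 weeks without re-treatment". Those who stop treatment before Week 48 (JNJ-6379 apart), "or who withdraw from the study prior to the given time point, will be considered as non-responders for FC in this study". Among those who remain, non-response is assigned to participants "with missing HBsAg assessment at that time after implementation of LOCF (as described in Section 5.4.2.1"), so the carry-forward step comes first.

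The HBeAg rule in SAP 5.4.2.3 has the same 12-week limit in follow-up but adds a second condition: "no value before the FU phase or more than 12 weeks prior to the respective time point will be used". The protocol (Appendix 1, Definitions of Terms) defines functional cure as "HBsAg seroclearance 24 weeks after end of treatment" and gives no carry-forward rule for it.

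**The concern.** Functional cure is a statement about HBsAg 24 weeks after treatment ends. If a value from 12 weeks can stand in for it, a participant can be counted as cured with no HBsAg observation in the second half of the period that the definition covers. Early off-treatment values may still carry drug effect. Protocol 2.2.2.1 reports that mean HBsAg in the earlier Phase 1/2a study reached its lowest point 8 weeks after the last JNJ-3989 injection. Protocol 4.2 sets a strict HBsAg cut-off for stopping NA because of the drug's direct effect on HBsAg.

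The result also feeds other analyses. Functional cure at off-treatment Week 24 is an outcome in the logistic regressions of SAP 5.5.2, and seroclearance at FU Week 24 is one of the blood endpoints in SAP Table 4.

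A second gap is that nothing in the HBsAg rule stops an on-treatment value from being carried into follow-up, although the HBeAg rule does stop this.

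**Working it through.** **Inputs.** Carry-forward limit: 12 weeks, inclusive, so 12 × 7 = 84 days (SAP 5.4.2.1). FU Week 12: target day 85, window 72–99. FU Week 24: target day 169, window 156–183 (SAP Table 2). Follow-up day 1 is the day after the open-label phase ends, which for a completer is the Week 48 visit; the 5-day extension is only for adverse events and concomitant medications (SAP Table 1). Follow-up day d is therefore d days after the Week 48 visit. Planned size: 12 per panel, 24 in Panels 1 and 2 (SAP 3).

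**Time scale.** SAP Table 2 labels FU Week 12 as Week 60 and FU Week 24 as Week 72. Check: 48 + 12 = 60 and 48 + 24 = 72. Both agree.

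**A 12-week value used at 24 weeks** (participant who stops everything at Week 48).
- Nominal weeks: 72 − 60 = 12, allowed.
- Target days: 169 − 85 = 84, allowed, exactly at the limit.
- Actual sample dates against day 169: a FU Week 12 sample on days 85–99 qualifies; one on days 72–84 is 85 to 97 days old and does not.

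**What has to be missing.** Carry-forward takes the latest value, so the Week 12 value decides the result only if Weeks 16, 20 and 24 are all missing. If Week 16 is present, the carried value is 169 − 113 = 56 days old; if Week 20 is present, 169 − 141 = 28 days. The participant must also be still in the study and not re-treated.

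**Direction.** Without carry-forward, SAP 5.4.2.5 would make the participant a non-responder. A carried value at or above the LLOQ leaves that unchanged; a carried value below it turns non-response into cure. Against the SAP's own default, the rule can only raise the count.

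**Size per participant** (exact two-sided 80% intervals).
- Of 24: 1/24 = 4.2 points. 0/24 is 0% (0 to 9.1); 1/24 is 4.2% (0.4 to 15.3).
- Of 12: 1/12 = 8.3 points. 0/12 is 0% (0 to 17.5); 1/12 is 8.3% (0.9 to 28.7).

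**A Week 48 value used at FU Week 12.** The Week 48 sample is on-treatment, because SAP 5.1.3 extends that period to 2 days after the last NA dose and 28 days after the last JNJ-3989 dose.
- Nominal weeks: 60 − 48 = 12, allowed.
- Strict days: 85 against a limit of 84, not allowed.

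The SAP does not say which count applies. For a participant off NA, the FU Week 2, 4, 8 and 12 results must all be missing.

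**The case against.** The strongest reply is that the rule will almost never act. Participants off NA are seen every 4 weeks (Protocol 6.6.2), with quantitative HBsAg scheduled at each follow-up visit (Protocol 1.3.2), and withdrawals are already non-responders for functional cure. Three results in a row must be missing in someone who stays in the study. That stands, and perhaps nobody will meet the condition. It is still possible: Protocol 7.2 says that declining visits is not necessarily withdrawal of consent, and the COVID-19 appendix provides for missed assessments.

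A second reply is that 12 weeks matches a real schedule. Participants who continue or restart NA and are stable come every 12 weeks (Protocol 1.3.2). That explains the limit for general follow-up seroclearance. It does not explain it for functional cure, which those participants cannot reach.

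Third, the primary endpoint is intrahepatic, and the study has no hypothesis and no formal test. That also stands: no error rate or sample size is affected.

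Four stronger readings are tempting, and the documents do not support them.
- *A Week 48 value definitely counts at FU Week 12.* It does so only on nominal weeks. Functional cure is not touched, and for participants still on NA the FU Week 12 value is on-treatment anyway.
- *About 4.6 of 24 participants are exposed* (24 × 0.191, from the 19.1% in the Amendment 4 rationale). That rate is for meeting the NA completion criteria, which need HBsAg below 10 IU/mL. Functional cure needs a value below 0.05 IU/mL, and the same rationale says that few participants reached seroclearance at Week 48.
- *A fixed share of on-time visits fails a literal 24-week test.* The ±4-day window gives days 165–173. On the SAP's day count, days 165–167 fall short of 24 × 7 = 168. But Protocol 1.3.2 schedules follow-up from the last JNJ-3989 dose (Week 44). On that anchor FU Week 24 is Week 68, only 20 weeks after Week 48, and every day in the window falls short. No single count can be given.
- *The FU Week 24 window is the right place to look for everyone.* It is not right for PegIFN-α2a participants who stop later (see the fix).

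**Conclusion.** The point holds in a limited form. As written, the SAP allows a value from 12 weeks off treatment to establish functional cure at 24 weeks, on nominal weeks and on target days alike. The condition is a participant who remains in the study, is not re-treated, and lacks the 16-, 20- and 24-week results. The documents give no basis for a probability, and the visit schedule suggests that it is small. When it happens, the count can only go up relative to the SAP's own default, by 4.2 points per participant with 24 or 8.3 points in a panel of 12. These sizes assume the planned numbers.

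The missing bar on values from before follow-up is a genuine inconsistency with the HBeAg rule. Its one concrete effect, a Week 48 value serving at FU Week 12, turns on 84 versus 85 days and touches only a descriptive proportion. SAP 5.4.2.1 has no withdrawal rule of its own, so on nominal weeks that effect could extend to a participant who left after Week 48 with HBsAg below the LLOQ.

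**What to change.** 1. **Functional cure:** do not use carry-forward. Require an observed HBsAg value in a stated analysis window around 24 (36, 48) weeks after the last dose of all study interventions, including NA and PegIFN-α2a; otherwise count the participant as a non-responder.
2. **Anchor:** tie that window to the stop of all interventions, not to FU Week 24. A participant who starts PegIFN-α2a just before Week 48 for 24 weeks stops near Week 48 + 24 = 72 and reaches 24 weeks off near Week 96, whereas FU Week 24 is Week 72. SAP Table 2 has no window on this anchor, so one must be added.
3. **Duration:** state that a visit inside the window meets the 24-week requirement, so that a visit held a few days early does not fail on a literal count.
4. **Other HBsAg follow-up time points:** add the HBeAg rule's bar on values from before the follow-up phase, and say whether the limit counts nominal weeks or actual days.

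The cost is SAP wording and the matching derivations. The downside is that a participant who misses the visit may become a non-responder despite being truly cleared.

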5.4.2.1.1. Time to HBsAg Seroclearance

Time to HBsAg seroclearance is defined as the number of days between the date of first study intervention intake and the date of the first occurrence of HBsAg seroclearance (i.e., the date of the first HBsAg seroclearance – the date of first study intervention intake + 1). The participants who withdrew early from the study before achieving HBsAg seroclearance or who did not achieve HBsAg seroclearance will be censored at the last available HBsAg assessment.

In addition, time to the first occurrence of HBsAg <10 IU/mL (i.e., the date of the first occurrence of HBsAg <10 IU/mL – the date of first study intervention intake + 1) and HBsAg <100 IU/mL (i.e., the date of the first occurrence of HBsAg <100 IU/mL – the date of first study intervention intake + 1) will also be evaluated.

The Kaplan-Meier method will be used to estimate and plot the cumulative incidence. The median time with 80% CI will be estimated using Kaplan-Meier method, if possible.

5.4.2.2. HBsAg Seroconversion

Seroconversion of HBsAg is defined as having achieved HBsAg seroclearance and appearance of anti-HBs antibodies.

The seroconversion will only be assessed at the time points when the anti-HBs antibodies assessment is available. If the HBsAg value is missing at that specific time point, then the non-missing lab test closest to that specific timepoint will be used. If the non-missing lab test before and after the specific timepoint fall equidistant from the target timepoint, the later one will be used to impute the missing value.

Appearance of anti-HBs antibodies is defined as a baseline anti-HBs antibodies (quantitative) <LLOQ and a post-baseline assessment \geq LLOQ. A sensitivity analysis will be conducted using the threshold of 10 mIU/mL, i.e., appearance of anti-HBs antibodies is defined as a baseline anti-HBs antibodies (quantitative) <10 mIU/mL and a post-baseline assessment \geq 10 mIU/mL.

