1.1. Objectives and Endpoints

1.1.1. For Panels 1 and 2

In Panels 1 and 2, the following objectives and endpoints will be assessed, overall and by study panel:

Objectives (Panels 1 and 2)	Endpoints (Panels 1 and 2)

Primary
 
 To assess changes in intrahepatic HBsAg between baseline and on-treatment liver biopsy in response to JNJ-3989-based combination treatment 	
 Changes in the proportion of HBsAg positive hepatocytes between baseline and on-treatment Week 40

Objectives (Panels 1 and 2)	Endpoints (Panels 1 and 2)
Secondary	

 To assess changes in intrahepatic immune response between baseline and on-treatment liver biopsy 	
 Changes between baseline and on-treatment liver biopsy in intrahepatic immune response (e.g., CD45+ T-cells, CD4+ T-cells, CD8+ T-cells, Natural Killer cells, and dendritic cells) in terms of proportion of cells, cell types, and spatial redistribution

 To assess changes in intrahepatic viral nucleic acids and proteins between baseline and on-treatment liver biopsy 	
 Changes from baseline in intrahepatic viral parameters (such as cccDNA, pgRNA, intrahepatic RNA, or HBsAg in terms of copy number, or number of positive cells) Changes from baseline in intrahepatic cccDNA levels and transcriptional activity (pgRNA/cccDNA ratio)

 To evaluate the efficacy of the study intervention as measured in the periphery 	
 The proportion of participants during the study intervention and follow-up phases with: 
 HBsAg seroclearance at Week 72 (i.e., 24 weeks after completion of all study interventions at Week 48) without restarting NA treatment. (Sustained) Reduction, suppression, and/or seroclearance considering single and multiple markers (such as HBsAg, HBeAg, HBV DNA and ALT) HBsAg and HBeAg seroconversion Flares (virologic, biochemical, and clinical) Time to first HBsAg seroclearance

 To evaluate the frequency of virologic breakthrough during study intervention 	
 Proportion of participants with virologic breakthrough

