6.2. Appendix 2 Changes to Protocol-Planned Analyses

No change from protocol-planned analyses.

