Type of NA at study entry (only for virologically suppressed participants): TD, TAF, ETV	

Continuous Variables	Summary Type
HBV viral activity and serology parameters	Frequency distribution with the number and percentage of participants in each category.
HBeAg status at study entry: positive, negative	
HBsAg category at baseline (IU/mL): < 500, < 1,000, < 10,000, ≥ 10,000	
HBV DNA category at baseline (IU/mL): < LLOQ Target detected (TD) or not detected (TND), < LLOQ TD, < LLOQ TND, < 60, < 2,000, < 20,000, < 100,000, ≥ 100,000	
HBV RNA category at baseline (copies/mL): TND, < Limit of Detection (LOD), < LLOQ, < 1,000, ≥ 1,000	
HBcrAg category at baseline (log U/mL): < 3, ≥ 3 - < 4, ≥ 4	
HBsAg Antibody (Anti-HBs) status at baseline: Positive, Negative	
HBsAg Antibody (Anti-HBs) category at baseline (mIU/mL): < 10, ≥ 10	
HBeAg Antibody (Anti-HBe) status at baseline: Positive, Negative	
Baseline ALT toxicity grade according to DAIDS	
Baseline ALT categorization: ≤ 1.0xULN, > 1.0xULN to <2.5xULN, ≥ 2.5x	
Stage of liver fibrosis: F0, F1, F2	

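### SAP seroconversion requires the antibody to be absent at baseline, which the protocol does not, and baseline antibody-positive participants stay in the denominator

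*SAP*

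**What the plan says.** Both documents name "HBsAg and HBeAg seroconversion" as a secondary endpoint, expressed as a proportion of participants.

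- **Protocol, Appendix 1, Definitions of Terms:** seroconversion is "HBsAg or HBeAg negativity and anti-HBs or anti-HBe antibody positivity, respectively". No condition is placed on the antibody at baseline.
- **SAP 5.4.2.2 (HBsAg):** "Seroconversion of HBsAg is defined as having achieved HBsAg seroclearance and appearance of anti-HBs antibodies". Appearance is then given a baseline condition: "Appearance of anti-HBs antibodies is defined as a baseline anti-HBs antibodies (quantitative) <LLOQ and a post-baseline assessment" at or above LLOQ. The next sentence adds a second threshold: "A sensitivity analysis will be conducted using the threshold of 10 mIU/mL", applied to both the baseline and the later value.
- **SAP 5.4.2.3 (HBeAg):** "Appearance of anti-HBe antibodies is defined as a baseline anti-HBe antibodies (qualitative) with a" negative result, followed by a positive result after baseline.
- **Denominators:** SAP 5.4 puts all secondary endpoints on the ITT set. SAP 5.4.2.3 limits HBeAg seroconversion to participants HBeAg positive at entry. Neither section mentions baseline antibody status when setting the denominator.
- **SAP Appendix 3, Table 9:** lists "HBsAg Antibody (Anti-HBs) status at baseline: Positive, Negative" among the baseline summaries, with a matching row for anti-HBe.
- **SAP Appendix 2:** "No change from protocol-planned analyses".

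On missing antigen values, SAP 5.4.2.2 and 5.4.2.3 fill seroconversion with the closest available result, before or after the visit. Seroclearance is handled by observed cases or by a time-limited LOCF.

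**The concern.** The two documents describe different endpoints under one name. The protocol asks whether antigen is gone and antibody is present. The SAP asks whether antigen is gone and antibody is newly present. The second question is reasonable, but only participants without the antibody at baseline can answer it. Leaving the others in the denominator scores them as failures by construction. The SAP takes the at-risk step elsewhere: ALT normalization in 5.4.2.4.5 is summarized only for participants with elevated ALT at baseline.

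With about 12 participants per panel, one changed classification is visible in the reported rate. HBsAg seroconversion at off-treatment Week 24 is also a listed outcome for the logistic models in SAP 5.5.2. A reader of the report who relies on the protocol definition and on Appendix 2 would not know that the tabulated quantity differs.

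The second strand is internal to the SAP. Seroconversion is meant to require seroclearance, but different missing-value rules allow the first without the second at the same visit.

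**Working it through.** The documents state no seroconversion rate or precision, so there is no figure to reproduce. The check compares the rules and then sizes one reclassification.

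**Inputs.** Anti-HBs LLOQ is 5 mIU/mL (SAP Table 3). Planned size is about 12 per panel, 24 in Panels 1 and 2 (SAP 1.2). The number of participants with antibody at baseline is not given. The protocol sets no anti-HBs threshold for positivity; LLOQ is assumed here.

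**Step 1: the rules applied to one participant.** Take HBsAg <LLOQ and a later anti-HBs of 50 mIU/mL.

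| Baseline anti-HBs (mIU/mL) | Protocol | SAP main | SAP sensitivity (10 mIU/mL) |
|---|---|---|---|
| 2.5 (imputed for <LLOQ) | yes | yes | yes |
| 6 | yes | no | yes |
| 9.9 | yes | no | yes |
| 10 | yes | no | no |

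A baseline of 5 to <10 fails the main definition but can pass the sensitivity analysis. A baseline of 10 or more fails both. For anti-HBe there is no second threshold: a positive baseline result always fails. That part concerns only participants HBeAg positive at entry, so Panel 2 is not affected.

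**Step 2: size.** One reclassified participant moves the rate by

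- 1/24 = 4.2 points for Panels 1 and 2 combined;
- 1/12 = 8.3 points for HBeAg in Panel 1.

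As an illustration, suppose 3 of 24 meet the protocol definition (3/24 = 12.5%), and *j* of those 3 had anti-HBs at or above LLOQ at baseline. Assume nobody else did.

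| *j* | Protocol | SAP as written | New appearance, at-risk denominator |
|---|---|---|---|
| 0 | 3/24 = 12.5% | 3/24 = 12.5% | 3/24 = 12.5% |
| 1 | 3/24 = 12.5% | 2/24 = 8.3% | 2/23 = 8.7% |
| 2 | 3/24 = 12.5% | 1/24 = 4.2% | 1/22 = 4.5% |

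Most of the difference comes from the numerator. Correcting the denominator alone does not recover the protocol's rate, so the two definitions have to be reported as two quantities.

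**Step 3: missing antigen values.** The schedules draw anti-HBs and anti-HBe at Day 1, Weeks 24 and 48, and Follow-up Weeks 4, 12, 24, 36 and 48.

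- *HBsAg.* SAP 5.4.2.1 allows LOCF at Weeks 40 and 48 (8 weeks back) and at Follow-up Weeks 12, 24, 36 and 48 (12 weeks back). Week 24 and Follow-up Week 4 are therefore observed-case. If HBsAg is missing at Week 24 and the nearest value, say Week 28, is <LLOQ, SAP 5.4.2.2 can use it. The participant can be seroconverted at Week 24 while not counted as cleared at Week 24.
- *HBeAg.* SAP 5.4.2.3 reports seroclearance both as observed case and with LOCF. Week 24 is observed-case in both. During follow-up, LOCF may not reach back before the follow-up phase or more than 12 weeks. The nearest-value rule for seroconversion carries neither limit and may also look forward.

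**The case against.** The strongest reply is that the protocol leaves detailed definitions to the SAP, and that requiring new antibody is a natural reading of conversion. No hypothesis is tested, and neither seroclearance nor Functional Cure uses antibodies. The SAP 5.5.2 associations may be assessed rather than must be, and their lists may change. All of this stands. It lowers the severity, and it means the point should not rest on which definition is the better main one. It does not remove the unrestricted denominator or the inaccurate statement in Appendix 2.

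Four stronger readings are tempting and are not supported.

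- *Baseline antibody-positive participants can never be counted.* For anti-HBs this is true of the main definition only; the 10 mIU/mL analysis admits those at 5 to <10.
- *Table 9 shows that such participants are expected.* A positive/negative row is a routine baseline category and says nothing about how many there will be.
- *The rate is capped well below 100%.* With 3 baseline-positive participants the ceiling would be 21/24 = 87.5%, but a ceiling matters only if the rate approaches it. The protocol's Amendment 4 rationale reports that only a limited number of participants in a related study cleared HBsAg at Week 48. If 2 of 24 clear and 3 of 24 are baseline-positive, independently, the expected loss is at most 2 × 3/24 = 0.25 participants, or 0.25/24 = about 1 point. Those counts are assumptions.
- *The missing-value mismatch is widespread.* Quantitative HBsAg is scheduled at every visit that draws anti-HBs, so it has to be missing while the antibody result is present. For HBsAg the clash falls mainly at Week 24 and Follow-up Week 4.

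**Conclusion.** The concern holds as a minor point. The SAP's seroconversion definition departs from the protocol's, Appendix 2 does not say so, and the denominators are not matched to the SAP's own definition. Under the main definition, participants with antibody at baseline can only lower the rate. Relative to the protocol definition the shift is always downward, by 4.2 points per reclassified participant overall or 8.3 points for HBeAg in Panel 1. It is zero if nobody who would meet the protocol definition has antibody at baseline, and the documents do not allow that number to be estimated. The sizes assume the planned 24 and 12 participants, and protocol positivity for anti-HBs at or above LLOQ.

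The missing-value mismatch is a separate wording fault. It is certain in the text and likely to be rare in the data. The low severity reflects an exploratory study and a descriptive secondary endpoint.

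**What to change.** 1. Report two rows for each antigen.
   - (a) Protocol definition: antigen <LLOQ and antibody positive at the same visit, regardless of baseline. Take anti-HBs positivity as at or above LLOQ, with 10 mIU/mL or more as the sensitivity threshold, and anti-HBe by the qualitative result. The protocol defines antigen negativity by the assay used, so state that <LLOQ is how the SAP implements it.
   - (b) New antibody appearance: the present SAP definition, with the denominator restricted to participants antibody-negative at baseline by the same threshold. For HBeAg, keep the restriction to HBeAg positive at entry as well.
2. For a missing antigen value at a seroconversion visit, apply the seroclearance rules: SAP 5.4.2.1 for HBsAg, and SAP 5.4.2.3 for HBeAg (observed-case and LOCF versions alike). Seroconversion is then always a subset of seroclearance.
3. State in SAP 5.5.2 which of these definitions the seroconversion outcome uses.
4. List the departure from the protocol definition in SAP Appendix 2.

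The cost is SAP wording and one extra table row per antigen. No new data are needed.
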